15.0 Recruitment Methods

15.1 Describe when, where, and how you will recruit potential subjects:

Paper flyers advertising the study will be posted throughout Williams Hall. In addition, this study will be advertised on the Psychology Department's participant recruitment system, called Sona. This recruitment method will begin immediately following IRB approval for the study, which is hoped to be obtained as soon as possible at the beginning of the Fall 2019 semester.

15.2 *Describe the source of subjects (for example, clinic patients with specific conditions, students in the library, community members at a gathering, or members of a local gym):*

The Sona system, which recruits undergraduate students currently taking a psychology class at VT.

15.3 *Describe the methods that you will use to identify potential subjects:*

Students clicking through the links on the Sona system and completing the prescreen survey will self-identify as a potential subject.

15.4 *Describe materials that you will use to recruit subjects. Attach copies of these documents with this protocol in Protocol Management and be sure to include the IRB protocol number on each document.*

- *For flyers, attach the final copy of printed flyers.*
- *For Virginia Tech News, Facebook postings and ads, newspaper ads, websites, MTurk/SONA/online survey systems, etc., attach the final wording and graphics to be used.*
- *For email recruitments, please include the subject line.*
- *For advertisements meant for audio broadcast, please submit the wording of the advertisement prior to taping (to avoid having to re-record with approved language) and submit the final recorded version for IRB review before use.*
- *Describe any compensation to subjects. Separate compensation into appropriate categories, such as: reimbursement for expenses, time and effort, and additional incentives for study participation. For each category, specify the amount (including any pro-rated amount), schedule, and method of payment.*

Flyer attachment, Sona final wording, and email are attached in Protocol Management. Compensation will be extra credit points awarded via the Sona system to the applicable psychology course as follows:

- 1.0 points for completion of the online prescreen
- (0.5 points for partial completion of the online prescreen)
- 0.5 points for arriving to the lab for the in-lab portion
- 0.5 points for completing the in-lab questionnaire portion of the study
- 0.5 points for completing the stimulus portion of the study
- 0.5 points for completing the remainder of the study including video review and post-hoc interview

16.0 Withdrawal of Subjects

16.1 Describe circumstances under which you anticipate subjects could be withdrawn from the research without their consent:

Subjects who have not complied with abstention requirements prior to arrival in the lab will be withdrawn without their consent upon determination of such non-compliance. Subjects who cannot remain still enough for a clean physiological signal to be obtained might be withdrawn without their consent. Before such withdrawal, subjects will be reminded to remain still in order to obtain a clean physiological signal.

16.2 If applicable, describe any procedures for orderly termination (e.g., discontinuation of a study drug or debriefing after a behavioral intervention):

Should participants ask to withdraw at any time during the in-lab portion, their request will be granted immediately. Any physiological equipment that had been attached will be carefully removed. Participants will be debriefed about the study goals and offered coaching on managing distress from the threat stimuli if they had reached this stage of the in-lab research. Participants will be invited but not required to express any concerns they had that led to their request.

16.3 Describe procedures that you will follow when subjects withdraw from the research, including partial withdrawal from procedures with continued data collection (e.g., participant declines to continue with regular blood draws, but continues with periodic behavioral questionnaires):

Same as 16.2. There is no way to partially withdraw from this study, so any withdrawal will be a full withdrawal.

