2.0 Objectives

2.1 *Describe the purpose, specific aims, or objectives of this study:*

The objectives of this study are to map patterns of mobility to patterns of physiology and self-reported subjective experience during a perceived threat experience.

2.2 *State the hypotheses to be tested:*

Mobility will be moderately positively correlated with SNS activation and moderately negatively correlated with PNS activation.

Transitions in mobility will be supported by ANS coactivation.

SNS activation will be moderately positively correlated with SUDS scores.

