3.0 Background

3.1 *Summarize the relevant prior research on this topic and gaps in current knowledge within the field of study:*

Defensive and survival behavior describes responses to perceived threat. Research in this area flourished in the 1990s and early 2000s, developing an empirically-validated model called the defense cascade (Lang, Bradley, & Cuthbert, 1997). This model has enormous potential to explain and predict behavior under stress and to improve psychotherapy. However, research on defensive behavior has stagnated over the last decade. I am proposing this research in hopes of breathing new life into this important but recently neglected area of research.

The defense cascade demonstrates six sequential survival strategies: freeze, flight, fight, fright, flag, and faint (Cannon, 1932, Blanchard & Blanchard, 1990, Bracha, 2004, Schauer & Elbert, 2010). Each stage is determined by a dynamic interaction with threat. Freeze, or attentive immobility, quiets the body to attend to a potential threat while minimizing predator detection of movement. As danger approaches, mobile defense is activated with flight, and continues into fight if escape options are eliminated. If the mobile defenses of flight or fight have failed, fright brings tonic immobility, preserving consciousness and muscle tone for vigilance and preparedness for the possibility of escape, while simultaneously quieting the movement and vocalization that would incite further predatory strike. In order to still the body during such seemingly terrifying moments, physiologically-driven changes include numbing physical pain (Ludäscher et al., 2007) and blunting emotions (Schmahl et al., 2006). If escape remains elusive, flag will reduce heart

rate to minimize blood loss from injury and transition to the final stage, faint (flaccid immobility), in which muscle tone and consciousness are lost. Faint conserves remaining resources for the potential of future escape, while maximizing dead-like appearance to become less interesting to a predatory threat.

The defense cascade illustrates dynamic switches between mobility and immobility. Yet in spite of its importance to defensive behavior, mobility has rarely been researched explicitly. Mobility therefore merits investigation as an explicit research variable.

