4.0 Study Endpoints

*4.1 Describe the primary and secondary **study** endpoints. See links below for discussion of study endpoints and how they may differ from study*

objectives. These are most common in clinical trials but are sometimes applicable to other types of biomedical research, as well as social, behavioral, or educational research. See link below for a discussion.

https://docs.google.com/document/d/1Wocz7K7a0hCQJPP0_khh5l1SQQjhGDDGHzcOPRHR5Tw/edit?usp=sharing

Primary endpoint will be the Pearson's correlations between the following variables:

- Mobility in X, Y, and Z planes each with pre-ejection period (PEP)
- Mobility in X, Y, and Z planes each with phasic electrodermal activity (EDA)

Secondary endpoint will be the Pearson's correlations between the following variables:

- Mobility in X, Y, and Z planes each with HF-HRV
- PEP and Subjective Unites of Distress Scale (SUDS)
- EDA and SUDS
- HF-HRV and PEP during one minute intervals where mobility is transitioning

- 4.2 *Describe any primary or secondary **safety** endpoints. These should be included for all studies that are greater than minimal risk. (Minimal risk: The probability and magnitude of harm or discomfort anticipated in the research that are not greater in and of themselves than those ordinarily encountered in daily life or during the performance of routine physical or psychological examinations or tests.):*

In order to minimize dangers associated with disoriented movement in the VR environment, one research assistant will be assigned the role of participant spotter, attending to any unsafe movements that participants may attempt while navigating their virtual environment.

Experiencing VR can increase the risk of dizziness or nausea because of the discrepancy between the actual and the virtual environment. The consent form includes a description of this possibility and how the participant can address it if they do not have tolerance of such symptoms.

The probability of psychological discomfort is assessed to be the same or less than that of watching a horror movie or playing a horror video game.

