14.0 Number of Subjects

14.1 *Indicate the total number of subjects to be enrolled and how this number was determined (e.g., sample size calculation [show], number of available subjects in a finite pool, number of tests funding award would allow):*

This study will seek to enroll 85 participants. A power analysis was calculated using the G*Power applet (Faul et al., 2007) to determine required sample size for a target correlation of 0.3. With $\alpha = 0.05$ and $\beta = 0.20$, the target effect size requires a sample size of at least 85 participants. It is estimated that 85 out of the 100 participants completing online screening will be in compliance with abstention requirements

14.2 If this is a multi-site study, indicate the number of subjects to be enrolled at this site and the total to be enrolled from all sites:

N/A

14.3 If applicable, indicate the number of potential subjects you expect to screen for enrollment, and the number of subjects you will need to complete the research procedures:

It is estimated that 200 subjects will be screened for enrollment in order to obtain 100 subjects to invite to the lab. Of these, we need 85 participants to follow abstention requirements and complete the research procedure.

14.4 If the study has more than one procedure, indicate the total number of subjects to undergo each procedure separately:

N/A

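### Section 16.1 lets staff tell participants to keep still and then withdraw those who cannot, in any phase, although mobility is the primary study variable

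*Protocol*

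**What the plan says.** Section 16.1 (Withdrawal of Subjects) gives staff a discretionary ground for removal: "Subjects who cannot remain still enough for a clean physiological signal to be obtained might be withdrawn without their consent". It adds a step that comes first: "Before such withdrawal, subjects will be reminded to remain still in order to obtain a clean physiological signal". Section 16.3 states: "There is no way to partially withdraw from this study, so any withdrawal will be a full withdrawal". Neither section gives a movement threshold, a duration or a study phase.

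Mobility is also the central variable. Section 3.1 says: "Mobility therefore merits investigation as an explicit research variable". The first hypothesis in Section 2.2 is: "Mobility will be moderately positively correlated with SNS activation and moderately negatively correlated with PNS activation". The primary endpoint in Section 4.1 consists of correlations of mobility on each of three axes with PEP and with phasic EDA, so mobility is in all six.

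The procedures in Section 8.1 expect movement. A creature appears to reach for the participant, a sudden vibration is delivered to the neck, a side camera is used to code movement toward or away from the stimulus, and the debrief asks about moments of high or low mobility. The only other posture instruction (Sections 8.3 and 21.1) is to stay seated, which is not the same as staying still.

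**The concern.** Two mechanisms act on the variable that the study sets out to measure.

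- **Selection.** The stated reason for withdrawal is failure to stay still, so those removed will tend to come from the upper end of mobility. If the relation is roughly linear between persons, cutting one tail of a variable narrows its spread and shrinks its correlations. Recruiting replacements restores the number of participants but not the spread.
- **Manipulation.** The reminder changes the mobility of those who stay. Nothing confines it to set-up. Given during the stimulus, it could itself produce a change in mobility, and one secondary endpoint in Section 4.1 is computed in the minutes when mobility is changing. Given in the 80 seconds after the noise burst, it would add a sensory input to a window that Section 8.1 keeps free of other sensory confounds.

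This is a rule of conduct. A later analysis plan cannot recover data that were never recorded, or undo an instruction given mid-stimulus.

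**Working it through.** **Inputs.** From Section 14.1: target correlation 0.3 (the power analysis was run "to determine required sample size for a target correlation of 0.3"), α = 0.05, β = 0.20, N = 85. Whether the test is one- or two-sided is not stated. The share withdrawn for movement is not stated either, so 1%, 5% and 10% are assumptions.

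**Step 1: the plan's own figure.** By Fisher z, N = ((z₀.₉₇₅ + z₀.₈₀)/atanh r)² + 3. With r = 0.3 this is ((1.960 + 0.842)/0.3095)² + 3 = 84.93, so 85. Power at 85 is 0.800. A one-sided test would need 68, so the plan's figure is two-sided. The sample-size arithmetic is sound.

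**Step 2: range restriction.** Take mobility as normal across persons, linearly related to the physiological index, and remove the top fraction q. With c = z₁₋q and λ = φ(c)/(1 − q):

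- variance ratio v = 1 − cλ − λ²
- restricted correlation r′ = r√v / √(1 − r² + r²v)
- power = Φ(atanh(r′)·√(85 − 3) − 1.960)

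For q = 10%: c = 1.2816, φ(c) = 0.1755 and λ = 0.1950. Then v = 1 − 0.2499 − 0.0380 = 0.712 and √v = 0.844. So r′ = 0.3 × 0.844 / √(0.91 + 0.09 × 0.712) = 0.2532/0.9870 = 0.256. Power = Φ(0.2624 × 9.055 − 1.960) = Φ(0.416) = 0.661.

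| Top movers removed | SD ratio √v | r′ | Power, 85 completers | Completers for 80% power |
|---|---|---|---|---|
| none | 1.000 | 0.300 | 0.800 | 85 |
| 1% | 0.968 | 0.291 | 0.775 | 91 |
| 5% | 0.900 | 0.272 | 0.715 | 104 |
| 10% | 0.844 | 0.256 | 0.661 | 118 |

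**Step 3: sensitivity to the model.** Section 16.1 says only that such participants might be withdrawn, so a sharp cut is the harsher case under normality. If half of the top 20% of movers are withdrawn (10% overall), r′ is 0.278 and power is 0.73. Skewness works the other way: with lognormal mobility, removing the top 5% gives r′ of about 0.16. The effect of the reminder is not in any of these figures, and the documents give nothing from which to quantify it.

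**The case against.** The strongest reply is that motion artefact is a real problem. The trigger is lack of a clean signal after a reminder, not movement as such, and a participant with no usable signal contributes no primary data pair. Keeping heavy movers with contaminated signals could also distort PEP, EDA and HF-HRV, and might inflate the correlations. All of this stands. It is why the rule should be confined to set-up rather than deleted, and why the artefact handling below is part of the remedy. It does not answer the point that the rule runs on into the stimulus period.

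A reader might also infer more than the documents support:

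- **Power is lost through a smaller sample as well.** At 10% removed and no replacement (76 completers), power would be 0.61. But Section 14.3 asks for 85 participants who complete the procedure, and Section 26.1 describes a large pool, so no-replacement figures do not follow. It is true that the 15-in-100 allowance in Section 14.1 covers abstention non-compliance only.
- **A few noisy minutes cost a whole participant.** The text describes those who cannot remain still enough after being reminded. Section 16.3 makes withdrawal full; it does not say that brief noise triggers it or that data already recorded are discarded.
- **Staff decide with the paired outcome in view.** Section 19.1 describes live monitoring as quality control, and Section 7.3 describes PEP and HF-HRV as calculated from recorded inputs. Nothing says those values are displayed live.
- **The correlations are certainly biased toward zero.** That needs a roughly linear between-person relation. Sections 4.1 and 5.2 do not say whether the correlations are between or within persons. If within, selection mainly limits who is represented, while the reminder still compresses measured mobility.

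**Conclusion.** The concern holds in this form: a discretionary keep-still reminder and full withdrawal, with no limit on phase, conflict with mobility being the primary variable. Following Section 16.1 as written selects on mobility and alters it during recording. Both follow from the text and need no distributional assumption.

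The size does need assumptions. On the between-person linear normal model with true r = 0.30 and 85 completers, the effect runs from slight (1% removed) to a loss of about 14 percentage points of power (10% removed: 0.800 − 0.661 = 0.139). It is smaller with partial selection and could be larger with skewed mobility. If almost nobody is withdrawn and no reminder is given during recording, it is negligible. Because the share is unknown, this is a change that should be made, not a demonstrated failure of the primary analysis.

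**What to change.** Amend Section 16.1 as follows.

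1. Limit the keep-still instruction and withdrawal for poor signal to the electrode check before physiological recording starts.
2. From the first baseline clip (the SUDS instructional video, when Section 8.1 starts recording), give no keep-still reminder and withdraw nobody for movement. Withdrawal at the participant's own request and the spotter's role in Section 4.2 are unaffected.
3. Keep all accelerometer data. Set unusable PEP, HF-HRV or EDA epochs to missing by a fixed artefact rule applied without regard to mobility or the paired values.
4. Report rejected epochs by mobility level, and the number and recorded mobility of anyone withdrawn.

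The cost is a few sentences of protocol text and some noisy or missing physiological epochs. Those epochs will be concentrated at high mobility, so selection is reduced, not removed; item 4 lets a reader see how much remains.

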17.0 Risks to Subjects

17.1 List the reasonably foreseeable risks, discomforts, hazards, or inconveniences to the subjects related the subjects' participation in the research. Include for the IRB's consideration a description of the probability, magnitude, duration, and reversibility of the risks. Consider physical, psychological, social, legal, privacy, and economic risks. Do not indicate "No risk" or "N/A." Instead, for studies with very low risk (e.g., anonymous online questionnaire on a mundane topic) indicate "The

investigators are not aware of any risks from participation in this study.” or “No more than risks than are found in everyday life.” The example consent form presents a tabular method for risk information, which you can also use here. Common risk types include:

- *Physical (e.g., potential for pain, discomfort, infection)*
- *Psychological (e.g., potential for stress, discomfort, and/or embarrassment)*
- *Social (e.g., potential for discrimination or stigmatization and disruption of personal and family relationships)*
- *Legal (e.g., potential for disclosure of illegal activity, negligence)*
- *Privacy (e.g., potential for personal information being accessed, used, or disclosed without the subjects’ knowledge or consent, breach of confidentiality/security)*
- *Economic (e.g., potential for individuals to lose access to economic services, employment, insurability)*

The online portion of the study is determined to have no more risks than are found in everyday life. The in-lab portion of the study is assessed to have the following risks:

Physical:

The single-use electrodes are affixed to participants' skin much as a Band-Aid would be affixed. The adhesive contained in the electrodes is about as strong as medical grade tape, so removing them may cause redness or irritation to the skin. The chances of such irritation are estimated to be 25% and the estimated duration of the discomfort is estimated to be 24 hours.

Virtual reality can cause dizziness or nausea because of the mismatch between the virtual and actual environment. Odds of such a reaction are estimated to be 25% and the estimated duration of such a response is 10 to 30 minutes.

Psychological: The main stimulus video portrays a threat that is approaching at an escalating rate. It is designed to activate the human defense cascade. Some individuals who are particularly sensitive to their own physiological responses might become distressed about their own physiological activation. The probability of such a reaction is estimated to be 5%. For participants who do have such a reaction, the duration of the reaction could be anywhere from 1 minute to 1 week. However, the threat stimulus is judged to be no more physiologically arousing than the average horror movie or horror video game.

The investigators are not aware of any risks from this study that fall into the categories of social, legal, privacy, or economic.

17.2 Indicate the measures you will use to minimize risks and monitor subjects for safety. (e.g., asking a subject at regular intervals to rate how they are feeling from 1 to 10, or to slowly crouch in order to check their balance.)

An explicit aspect of the study design is the frequent request for the participant's SUDS rating (1 to 10 scale expressing how distressed they are feeling). These SUDS requests will occur every minute throughout the stimulus portion of the study. Therefore, researchers will have a regular update to indicate degree of participant distress.

17.3 If applicable, indicate which procedures might have risks to the subjects that are currently unforeseeable. This will be rare, and usually applicable when testing a new drug or device or a new use of an existing drug or device:

N/A

17.4 If applicable, indicate which procedures might have risks to an embryo or fetus should the subject be or become pregnant:

N/A

17.5 If applicable, describe risks to others who are not subjects (e.g., collection of sensitive health data that might affect sexual partners if disclosed, mandatory reporting of abuse, DNA testing that might affect family members or relationships):

N/A

18.0 Potential Benefits to Subjects

18.1 Describe the potential benefits that individual subjects might experience from participating in the research. Include the probability, magnitude, and duration of the potential benefits, as this will be useful to the IRB's risk:benefit analysis. Do not include benefits to society or others. Do not list monetary or non-monetary compensation for participation, as this is not a benefit. These should be included in section 2 or 3 of this document:

It is hypothesized that SUDS requests do more than just help researchers or therapists to gauge their participant or client's well-being. The very nature of taking an emotionally-charged experience of distress and making it objective by giving it a number, can be a powerful neutralizer to fear and distress. There is an estimated 10% chance that participants will recognize this process as potentially useful for future distressing situations. For this reason, the study explicitly adds a second MAIA questionnaire at the end of the study to determine if the SUDS process changed participant's interoceptive awareness during the course of the study.

18.2 *If applicable, specify that there are no anticipated direct benefits for participants:*

N/A

